1.2 Secondary Objectives

- To evaluate the pharmacokinetic profiles of CB-5339
- To assess the preliminary antitumor activity of CB-5339 in patients with advanced solid tumors and lymphomas. Although the clinical benefit of this agent has not been established, the intent of offering this treatment is to provide a possible therapeutic benefit, and thus the patient will be carefully monitored for tumor response and symptom relief in addition to safety and tolerability.
- To determine the effects of CB-5339 on the ubiquitin proteasome system and on markers of cell death in pre- and post-treatment tumor biopsies and PBMCs

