2.2 CB-5339

CB-5339 is Cleave Therapeutics' second generation small-molecule inhibitor of p97. Its activity is due to binding and inhibition of the D2 ATPase domain of p97, resulting in the disruption of

ubiquitin proteasome system (UPS), the accumulation of cellular polyubiquitinated proteins, and consequent ER stress and activation of the unfolded protein response (UPR) (Anderson et al., 2015; Le Moigne et al., 2017; Magnaghi et al., 2013; Zhou et al., 2015). Cells exposed to CB-5339 ultimately undergo apoptosis by failing to restore protein homeostasis.

Cleave Therapeutics' first-in-class inhibitor of p97, CB-5083 (Anderson et al., 2015), was evaluated in two phase 1 dose-escalation trials in patients with advanced metastatic solid tumors (NCT02243917) and lymphoid malignancies (NCT02223598); no complete or partial responses were noted in the trials, although several patients remained on study for > 4 months with 11 months being the longest duration of treatment. Clinical development of CB-5083 was halted due to off-target inhibition of retinal phosphodiesterase 6 (PDE6), resulting in dose-limiting visual symptoms in patients on both trials. CB-5339 has a similar structure but different physicochemical properties to CB-5083 (Figure 2). As will be described in greater details below, CB-5339 has similar efficacy to CB-5083 in preclinical models but drug metabolism and pharmacokinetic studies show a 40-fold reduced effect on PDE6, 10-fold decreased potency on PDE6, and 4-fold lower retinal penetration when compared to CB-5083 (Figure 9).

[figure not shown]

Figure 2: CB-5083 (first generation inhibitor) and the current p97 inhibitor CB-5339 have similar structures but different physicochemical properties

Compound	p97 IC50 (nM)	MW	log P	H-bond donors	H-bond acceptors	pKa	pKa type	PSA (Å²)
CB-5339	9 nM	412.49	3.57	3	5	6.56	Basic	97.86
CB-5083	11 nM	413.47	2.72	2	5	4.74	Basic	95.06

Pharmacodynamic (PD) biomarkers for p97 inhibition on this study include K48-ubiquitinated proteins in the cytosol, nuclear accumulation of the pro-apoptotic transcription factor CHOP (indicative of unfolded protein response [UPR] and ER stress), and cleaved caspase-3 as an indicator of apoptosis.

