3. PATIENT SELECTION

3.1 Eligibility Criteria

- 3.1.1 Patients with histologically documented metastatic or locally advanced (not amenable to surgery) solid tumors whose disease has progressed on standard therapy or for which there is no available standard therapy or therapy known to prolong survival; or aggressive lymphoma who have refused or have no remaining curative options (e.g., stem cell transplant). Patients with indolent lymphomas must have undergone 3 or more prior regimens of therapy.
- 3.1.2 Any prior therapy must have been completed ≥ 4 weeks (6 weeks for nitrosoureas and mitomycin C) or, if known, ≥ 5 half-lives of the prior agent (whichever is shorter) prior to enrollment on protocol (minimum of 1 week between prior therapy and study enrollment), and the participant must have recovered to eligibility levels from prior toxicity. Prior definitive radiation should have been completed ≥ 4 weeks or palliative radiation should have been completed ≥ 2 weeks prior to study enrollment and all associated toxicities resolved to eligibility levels (patients on study may be eligible for palliative radiotherapy to non-targeted lesions after 2 cycles of therapy at the PI's discretion). Patients must be ≥ 2 weeks since any investigational agent administered as part of a Phase 0 study (where a sub-therapeutic dose of drug is administered) at the PI's discretion and should have recovered to grade 1 or baseline from any toxicities.
- 3.1.3 Patients who have had prior monoclonal antibody therapy must have completed that therapy ≥ 6 weeks (or 3 half-lives of the antibody, whichever is shorter) prior to enrollment on protocol (minimum of 1 week between prior therapy and study enrollment).
- 3.1.4 Age ≥ 18 years. Because no dosing or adverse event data are currently available on the use of CB-5339 in patients <18 years of age, children are excluded from this study, but will be eligible for future pediatric trials.
- 3.1.5 ECOG performance status ≤ 2 (Karnofsky $\geq 60\%$, see Appendix A) and life expectancy > 3 months,
- 3.1.6 Patients must have adequate organ and marrow function as defined below:
 - absolute neutrophil count $\geq 1,500/\text{mcL}$
 - platelets $\geq 100,000/\text{mcL}$ (solid tumor patients)
 $\geq 75,000/\text{mcL}$ (lymphoma patients)
 - total bilirubin $\leq 1.5 \times$ institutional upper limit of normal (ULN)
 - AST(SGOT)/ALT(SGPT) $\leq 3 \times$ institutional ULN
 - creatinine $\leq 1.5 \times$ institutional ULN

OR

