5.1 Agent administration

CB-5339 will be administered once daily, 4 days on and 3 days off, in 28-day cycles. CB-5339 capsules should be taken in a fasted state, either 1 hour before or 2 hours after meals. Patients have a 6-hr window to make up for missed/vomited doses.

Reported adverse events and potential risks are described in [Section 9](#). Appropriate dose modifications are described in [Section 5.9](#). No investigational or commercial agents or therapies other than those described below may be administered with the intent to treat the patient’s malignancy.

After cycle 2, as a measure of patient compliance only, a cycle will be considered completed if 90% of the prescribed CB-5339 doses are administered.

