5.4 General Concomitant Medication and Supportive Care Guidelines

All patients will be provided with the best available supportive care. All concurrent medications should be documented prior to initiation of treatment and periodically reviewed with the patient.

It is not known which CYP enzymes are involved in the metabolism of CB-5339, and CB-5339 appears to be a potential inhibitor of **CYP2C19** and 2C9 in vitro. Therefore, for patients enrolled in the dose-escalation phase, avoid concomitant use of drugs that are strong inhibitors of CYP enzymes during the dose escalation phase, and substrates of CYP2C19 and 2C9 with narrow therapeutic indices, as this may affect the determination of the recommended phase 2 dose.

During the expansion phase, any concomitant use of CB-5339 and drugs that are strong inhibitors of CYP enzymes or substrates with narrow therapeutic indices for CYP2C19 (e.g., diazepam) or CYP2C9 (e.g., warfarin, phenytoin, many sulfonylureas (tolbutamide, glyburide, glibenclamide, glipizide, glimepiride) will be monitored closely. Consult <http://medicine.iupui.edu/flockhart/> for frequently updated information on drug interactions with cytochrome P450 isoenzymes.

Patients on study may be eligible for palliative radiotherapy to non-targeted lesions after completing 2 cycles of therapy at the Principal Investigator's discretion.

- 5.4.1 Nausea/Vomiting: Anti-emetics will not be administered routinely prior to CB-5339. However, if a patient develops nausea/vomiting, anti-emetics such as but not limited to prochlorperazine, metoclopramide, 5-HT3 antagonists, or aprepitant may be given. In addition, if a patient develops nausea and/or vomiting that is Grade 2 or greater, anti-emetics may be instituted prophylactically at the discretion of the investigator. Nausea and vomiting will be considered refractory if it does not resolve to grade 2 or less with a combination of at least 2 anti-emetics within 24 hours.

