11.1.4 Response Criteria

Evaluation of Target Lesions

Complete Response (CR): Disappearance of all target lesions. Any pathological lymph nodes (whether target or non-target) must have reduction in short axis to <10 mm (<1 cm).

Partial Response (PR): At least a 30% decrease in the sum of the diameters of target lesions, taking as reference the baseline sum diameters.

Progressive Disease (PD): At least a 20% increase in the sum of the diameters of target lesions, taking as reference the smallest sum on study (this includes the baseline sum if that is the smallest on study). In addition to the relative increase of 20%, the sum must also demonstrate an absolute increase of at least 5 mm (0.5 cm). (Note: the appearance of one or more new lesions is also considered progressions).

Stable Disease (SD): Neither sufficient shrinkage to qualify for PR nor sufficient increase to qualify for PD, taking as reference the smallest sum diameters while on study.

Evaluation of Non-Target Lesions

Complete Response (CR): Disappearance of all non-target lesions and normalization of tumor marker level. All lymph nodes must be non-pathological in size (<10 mm [<1 cm] short axis).

Note: If tumor markers are initially above the upper normal limit, they must normalize for a patient to be considered in complete clinical response.

Non-CR/Non-PD: Persistence of one or more non-target lesion(s) and/or maintenance of tumor marker level above the normal limits.

Progressive Disease (PD): Appearance of one or more new lesions and/or *unequivocal progression* of existing non-target lesions. *Unequivocal progression* should not normally trump target lesion status. It must be representative of overall disease status change, not a single lesion increase.

Although a clear progression of “non-target” lesions only is exceptional, the opinion of the treating physician should prevail in such circumstances, and the progression status should be confirmed at a later time by the review panel (or Principal Investigator).

Evaluation of Best Overall Response

The best overall response is the best response recorded from the start of the treatment until disease progression/recurrence (taking as reference for progressive disease the smallest measurements recorded since the treatment started). The patient's best response assignment will depend on the achievement of both measurement and confirmation criteria.

For Patients with Measurable Disease (i.e., Target Disease)

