Target Lesions	Non-Target Lesions	New Lesions	Overall Response	Best Overall Response when Confirmation is Required*
CR	CR	No	CR	≥4 wks. Confirmation**
CR	Non-CR/Non-PD	No	PR	≥4 wks. Confirmation**
CR	Not evaluated	No	PR	
PR	Non-CR/Non-PD/not evaluated	No	PR	Documented at least once ≥4 wks. from baseline**
SD	Non-CR/Non-PD/not evaluated	No	SD	
PD	Any	Yes or No	PD	no prior SD, PR or CR
Any	PD***	Yes or No	PD	
Any	Any	Yes	PD	

* See RECIST 1.1 manuscript for further details on what is evidence of a new lesion.

** Only for non-randomized trials with response as primary endpoint.

*** In exceptional circumstances, unequivocal progression in non-target lesions may be accepted as disease progression.

Note: Patients with a global deterioration of health status requiring discontinuation of treatment without objective evidence of disease progression at that time should be reported as

“*symptomatic deterioration.*” Every effort should be made to document the objective progression even after discontinuation of treatment.

For Patients with Non-Measurable Disease (i.e., Non-Target Disease)

Non-Target Lesions	New Lesions	Overall Response
CR	No	CR
Non-CR/non-PD	No	Non-CR/non-PD*
Not all evaluated	No	not evaluated
Unequivocal PD	Yes or No	PD
Any	Yes	PD

* ‘Non-CR/non-PD’ is preferred over ‘stable disease’ for non-target disease since SD is increasingly used as an endpoint for assessment of efficacy in some trials so to assign this category when no lesions can be measured is not advised

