11.2.1 CT/MRI measurements

Assessment of tumor burden will use the sum of the longest diameters (SLD). In subjects with disseminated disease, a maximum of 3 target lesions should be selected to estimate tumor response.

Target lesions should be selected per the following criteria:

- Target lesions should be selected from lesions of the largest size that can be measured reproducibly and preferably representing multiple sites and organs.
- Lymph nodes:
 - Lymph nodes can be considered target lesions if the lymph node longest diameter measures ≥ 15 mm.
 - A lymph node measuring between 10 and 14 mm is considered abnormal but should

not be selected as a target lesion.

- Lymph nodes measuring <10 mm in diameter are considered normal and cannot be used as target lesions.
 - In certain anatomical sites (inguinal, axillary, and portacaval), normal lymph nodes may exist in a narrow, elongated form, and such nodes should not be selected as target lesions if alternatives are available.
- Extranodal lesions are selected as target lesions if they have a soft tissue component, based on their size and the ease of reproducibility of repeated measurements, with a minimum measurement of the longest diameter of ≥ 15 mm.
- Nontarget lesions:
 - All other lesions should be identified as nontarget lesions and should be recorded at baseline, without the need to measure them.
 - Nontarget lesions should be followed and reported as present, absent, or clear progression.

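### Palliative radiotherapy to non-target lesions is allowed on study with no scoring rule, so it can deepen a response to CR or prolong stable disease and response duration

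*Combined protocol and SAP*

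**What the plan says.** **Permission.** Section 5.4: "Patients on study may be eligible for palliative radiotherapy to non-targeted lesions after completing 2 cycles of therapy", at the Principal Investigator's discretion. Section 3.1.2 agrees: "patients on study may be eligible for palliative radiotherapy to non-targeted lesions after 2 cycles of therapy at the PI's discretion". The general restriction in Section 5.1 does not remove this permission, because it exempts what the protocol goes on to describe: "No investigational or commercial agents or therapies other than those described below may be administered with the intent to treat" the malignancy.

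**Endpoint.** A secondary objective in Section 1.2 is: "To assess the preliminary antitumor activity of CB-5339 in patients with advanced solid tumors and lymphomas". Section 2.3 also names patient responses as one of three determinants of the RP2D.

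**Scoring in solid tumors.** Section 11.1.2 classes every lesion that is not a target lesion as non-target, and has each one followed for the whole of follow-up. In Section 11.1.4, non-target CR means "Disappearance of all non-target lesions and normalization of tumor marker level". Persistence is Non-CR/Non-PD, and unequivocal progression is PD. These calls feed the overall response. Section 11.1.5 runs the duration of response and of stable disease to progression, with no censoring event.

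**Scoring in lymphoma.** Section 11.2.1: "Nontarget lesions should be followed and reported as present, absent, or clear progression".

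**Analysis set.** Section 8.3.1 puts all eligible patients in the main response analysis, with a possible exception only for those never dosed.

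**The concern.** The stated question is the activity of CB-5339. Sections 3.1.2 and 5.4 keep radiotherapy away from target lesions only, while non-target lesions remain part of the response call. Radiotherapy is given to lesions that trouble the patient, so it is related to the outcome being measured. Its effect on an irradiated lesion is in the favourable direction: toward disappearance, or away from visible progression.

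The trial has one arm, so no comparison would show the contribution of radiotherapy. If irradiated lesions are scored like any other, part of what is reported as CR, stable disease or duration describes drug plus radiotherapy. The plan neither states this as its intention nor gives a way to separate the two.

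**Working it through.** The plan gives no target response rate, power for response or expected frequency of radiotherapy, so there is no planned figure to reproduce. The check applies the plan's own response tables.

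**Step 1: measurable disease, no new lesions (Section 11.1.4).** The table has no row for target PR or SD with non-target CR. I read these as PR and SD, since the target lesions then limit the call.

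| Target | Non-target CR | Non-CR/Non-PD | Not evaluated | PD |
|---|---|---|---|---|
| CR | CR | PR | PR | PD |
| PR | PR | PR | PR | PD |
| SD | SD | SD | SD | PD |
| PD | PD | PD | PD | PD |

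- Target CR: if radiotherapy clears the last non-target lesion, the overall call moves from PR to CR.
- Target PR or SD: the same clearance changes nothing.
- Target CR, PR or SD: if radiotherapy keeps non-target disease at Non-CR/Non-PD when it would have become PD, the overall call is PR, PR or SD instead of PD.
- Target PD: always PD.

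**Step 2: non-measurable disease only (second table in Section 11.1.4).** Non-target CR with no new lesion is overall CR directly. Such patients can enter: Section 3.1 does not require measurable disease, and Section 3.4.1 asks only that it be evaluated. Section 11.1.1 limits the group evaluable for objective response to measurable disease, but Section 8.3.1 includes all eligible patients. The two sections are not reconciled, so this route is open under 8.3.1.

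**Step 3: durations (Section 11.1.5).** Both durations end at progression. If radiotherapy prevents non-target progression from appearing, neither clock stops unless target lesions grow or a new lesion appears.

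**Step 4: lymphoma (Section 11.2.4).** The category table has no non-target row. CR depends on target lesions, nodal size, FDG-PET normalization and marrow. An irradiated site can therefore matter only through nodal or PET normalization, for example when a target PR with a normalized PET is called CR.

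**Step 5: timing.** Two cycles are 2 × 28 = 56 days, or 8 weeks, and restaging is every 8 weeks (Section 11). The first restaging is unaffected if it precedes radiotherapy, but the plan does not fix that order. DLTs (cycle 1) and the paired biopsies (baseline and cycle 1 day 1) come before any permitted radiotherapy.

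**Step 6: weight of one patient.** One reclassified patient shifts the proportion in a category, such as CR, by 1/n:
- expansion cohort: 1/15 = 6.7 points
- planned minimum evaluable: 1/21 = 4.8 points
- planned maximum evaluable: 1/33 = 3.0 points

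**Step 7: does scoring as not evaluated suffice?** From the table, target CR with not evaluated gives PR, so the upgrade to CR is blocked. In non-measurable disease the call becomes not evaluated. But target SD with not evaluated is still SD, so a separate duration rule is needed.

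**The case against.** The strongest case on the other side is that this is a small clarification to a secondary, descriptive endpoint. Much of it stands.

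- **Creating responders.** A reader might infer that one irradiated lesion could take a cohort from no responders to one (0/15 to 1/15, or 0/33 to 1/33), which would look striking beside the CB-5083 experience, where "no complete or partial responses were noted in the trials". For measurable disease the table does not support this: the upgrade needs target CR, and that patient is already a responder, so CR+PR is unchanged. Only the non-measurable route could do it, and it also needs every lesion gone, normal tumor markers and no new lesion. The CB-5083 result is background, not a planned comparator.
- **Hiding progression.** A reader might infer that any growing lesion escapes PD once irradiated. Section 11.1.4 requires a change in overall disease status, so growth in one non-target lesion is not normally PD. Progression already on a scan is already scored. What remains is progression that radiotherapy prevents before a scan shows it.
- **Length of the effect.** A reader might infer that each masked progression adds at least one 8-week restaging interval. Target growth or a new lesion at the same scan would give PD and add nothing.
- **Lymphoma.** A reader might infer from 11.2.1 that non-target lesions decide CR and PD. That section only has them followed and reported.
- **A rule elsewhere.** Sections 11.1 and 11.2 adopt RECIST 1.1 and RECIL 2017, which are not reproduced in full. The protocol text carries no rule for irradiated lesions. Section 5.7 takes patients off study when they receive standard of care, but does not say that this radiotherapy counts, and 3.1.2 and 5.4 describe patients who are on study.

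These points limit the size. They do not supply a scoring rule.

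**Conclusion.** The concern holds in a bounded form. The permission in 3.1.2 and 5.4, combined with the scoring in 11.1.2, 11.1.4 and 11.1.5, lets radiotherapy:

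- (a) upgrade PR to CR when the target lesions are already in CR;
- (b) give a CR in a patient with only non-measurable disease, who counts under 8.3.1;
- (c) prevent non-target progression from being seen, so that SD or response duration runs on.

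The effect falls mainly on CR depth and durations. The overall response rate is exposed through (b) and, less directly, where prevented progression leaves a response standing. The primary DLT assessment and the paired biopsies are not affected, but responses are among the RP2D considerations in Section 2.3, so the matter is more than cosmetic.

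The number of irradiated patients is unknown. The 3.0 to 6.7 points in the working are the weight of one patient, not a forecast. The conclusion assumes that non-targeted in 3.1.2 and 5.4 means non-target as defined in 11.1.2, and that at least one patient is irradiated. It takes no position on whether radiotherapy should be permitted.

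**What to change.** Leave the permission as it stands and add analysis rules:

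1. **CRF:** record each irradiated lesion and the date of radiotherapy.
2. **11.1.4:** from that date, score an irradiated non-target lesion as not evaluated, so that it cannot support CR. For patients with only non-target disease, take best response from assessments before radiotherapy.
3. **11.1.5:** censor SD and response duration at the last assessment before radiotherapy. Because that censoring may be informative, add a sensitivity analysis that counts radiotherapy as progression.
4. **11.2:** state that nodal or FDG-PET normalization at an irradiated site does not by itself support CR.
5. **8.3.1:** list the irradiated patients alongside the response results.

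The cost is a few sentences and two recorded items per irradiated lesion, with no extra scans or patients. The downside is that a few patients may have a less favourable best response or a shorter duration.

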5.5 Duration of Therapy

In the absence of treatment delays due to adverse event(s), treatment may continue until one of the following criteria applies:

- Disease progression
- Intercurrent illness that prevents further administration of treatment
- Significant toxicity occurs despite 2 dose reductions or no lower dose level exists,
- Patient decides to withdraw from the study
- General or specific changes in the patient's condition render the patient unacceptable for further treatment in the judgment of the investigator
- Patient non-compliance
- Pregnancy
- Termination of the study by sponsor
- The drug manufacturer can no longer provide the study agent

The reason(s) for protocol therapy discontinuation, the reason(s) for study removal, and the corresponding dates must be documented in the Case Report Form (CRF).

